4.2 Secondary objectives and measurements

Objectives	Measurement
Improved control of asthma symptoms as measured by the Asthma Control Test	Changes in the Asthma Control Test from baseline to 13 and 26 weeks (for asthma patients)
Improved control of COPD symptoms as measured by the COPD Assessment Test	Changes in the COPD Assessment Test from baseline to 13 and 26 weeks (for COPD patients and patients with both asthma and COPD)
Improved adherence to asthma medication, as indicated by an increase in the frequency with which patients request to refill preventer inhaler prescriptions.	Reduction in the number of days between consecutive preventer inhaler prescription requests from baseline to 13 and 26 weeks
Difference in emergency admissions	Differences in the number of emergency admissions between the intervention and control group over 26 weeks
Differences in NHS utilisation	Differences in the utilisation of NHS resources between the intervention and control group over 26 weeks

The complete survey questionnaire that will be administered to participants can be found in Appendix 7. This appendix includes the full survey questionnaire for (1) asthma and (2) COPD patients, including symptom control as measured through the ACT (for asthma) or CAT (for COPD), medication adherence as measured through the MARS-5 and NHS utilisation questions as measured through a number of questions.

Protocol: 22 November 2022, v2.0

IRAS ID: 316452

11

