- 11. Roughly how many times have you stayed in hospital in relation to your asthma over the past 3 months, if at all?

Put '0' if you haven't had to stay in hospital at all in relation to your COPD over the past 3 months. If you don't remember the exact number, please just put your best guess.

- a. Free text box
- 12. Roughly how many times have you attended an emergency GP appointment with your own GP or a walk-in centre in relation to your asthma over the past 3 months, if at all?

Put '0' if you haven't had to use this service at all in relation to your asthma over the past 3 months. If you don't remember the exact number, please just put your best guess.

- a. Free text box
- 13. Roughly how many times have you called the NHS 111 helpline in relation to your asthma over the past 3 months, if at all?

Put '0' if you haven't had to use this service at all in relation to your asthma over the past 3 months. If you don't remember the exact number, please just put your best guess.

- a. Free text box
- 14. Roughly how many times have you visited an Urgent Care Centre in relation to your asthma over the past 3 months, if at all?

Put '0' if you haven't had to use this service at all in relation to your asthma over the past 3 months. If you don't remember the exact number, please just put your best guess.

- a. Free text box
- 15. Roughly how many times have you visited Accident & Emergency (A&E) in relation to your asthma over the past 3 months, if at all?

Put '0' if you haven't had to use this service at all in relation to your asthma over the past 3 months. If you don't remember the exact number, please just put your best guess.

a. Free text box

Protocol: 22 November 2022, v2.0

Com	olete	que	stionnaire for COPD patients		
1.	1. How often do you cough?				
		a.	0 - I never cough		
		b.	1		
		C.	2		
		d.	3		
		e.	4		
		f.	5 - I cough all the time		
2.	. Ho	How much phlegm (mucus) do you feel you have on your chest?			
		a.	0 - I have no phlegm (mucus) on my chest at all		
		b.	1		
		C.	2		
		d.	3		
		e.	4		
		f.	5 - My chest is completely full of phlegm (mucus)		
3.	. Ho	ow tig	ht is your chest?		
		a.	0 - My chest does not feel tight at all		
		b.	1		
		C.	2		
		d.	3		
		e.	4		
		f.	5 - My chest feels very tight		
4.	. W	hen d	o you get out of breath?		
		a.	0 - When I walk up a hill or one flight of stairs I am not breathless		
		b.	1		
		C.	2		

Protocol: 22 November 2022, v2.0

	d.	3		
	e.	4		

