	f.	5 - When I walk up a hill or flight of stairs I am completely out of breath		
5.	How mu	uch are you limited by your COPD when at home?		
	a.	0 - I am not limited doing any activities at home		
	b.	1		
	C.	2		
	d.	3		
	e.	4		
	f.	5 - I am very limited doing activities at home		
6.	How confident do you feel leaving your home?			
	a.	0 - I am confident leaving my home despite my lung condition		
	b.	1		
	C.	2		
	d.	3		
	e.	4		
	f.	5 - I am not confident leaving my home at all because of my lung condition		
7.	How we	ell do you sleep?		
	a.	0 - I sleep soundly at night		
	b.	1		
	C.	2		
	d.	3		
	e.	4		
	f.	5 - I do not sleep soundly because of my lung condition		
8.	B. How much energy do you have?			
	a.	0 - I have lots of energy		
	b.	1		
	C.	2		

Protocol: 22 November 2022, v2.0

d. 3 e. 4 f. 5 - I have no energy at all 9. During the past 2 weeks, how often did you forget to take your regular inhaler? a. Always b. Often c. Sometimes d. Rarely e. Never 10. During the past 2 weeks, how often did you alter the dose of your regular inhaler? a. Always b. Often c. Sometimes d. Rarely e. Never 11. During the past 2 weeks, how often did you stop taking your regular inhaler for a while? a. Always b. Often c. Sometimes d. Rarely e. Never 12. During the past 2 weeks, how often did you miss out a dose? a. Always b. Often c. Sometimes d. Rarely e. Never

Protocol: 22 November 2022, v2.0

- 13. During the past 2 weeks, how often did you take less regular inhaler than instructed?
 - a. Always
 - b. Often
 - c. Sometimes
 - d. Rarely
 - e. Never
- 14. Roughly how many times have you stayed in hospital in relation to your COPD over the past 3 months, if at all?

Put '0' if you haven't had to stay in hospital at all in relation to your COPD over the past 3 months. If you don't remember the exact number, please just put your best guess.

- a. Free text box
- 15. Roughly how many times have you attended an emergency GP appointment with your own GP or a walk-in centre in relation to your COPD over the past 3 months, if at all?

Put '0' if you haven't had to use this service at all in relation to your asthma over the past 3 months. If you don't remember the exact number, please just put your best guess.

- a. Free text box
- 16. Roughly how many times have you called the NHS 111 helpline in relation to your COPD over the past 3 months, if at all?

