Put '0' if you haven't had to use this service at all in relation to your asthma over the past 3 months. If you don't remember the exact number, please just put your best guess.

- a. Free text box
- 17. Roughly how many times have you visited an Urgent Care Centre in relation to your COPD over the past 3 months, if at all?

Put '0' if you haven't had to use this service at all in relation to your asthma over the past 3 months. If you don't remember the exact number, please just put your best guess.

- a. Free text box
- 18. Roughly how many times have you visited Accident & Emergency (A&E) in relation to your COPD over the past 3 months, if at all?

Put '0' if you haven't had to use this service at all in relation to your asthma over the past 3 months. If you don't remember the exact number, please just put your best guess.

a. Free text box

Protocol: 22 November 2022, v2.0

Protocol Title: A randomised controlled trial to evaluate the impact of supportive text messages from GP practices on self-reported symptoms and inhaler adherence in patients with asthma and/or chronic obstructive pulmonary disease (COPD) who have been prescribed a preventer (daily) inhaler (Inhaler Trial)

Protocol no: Accurx-001

COMMERCIAL PARTICIPANT IDENTIFICATION CENTRE AGREEMENT

Between

Accurx Ltd, [name]

"Participating Organisation"

AND

GP Practice as detailed in the "Principal Investigator and Service Agreement for the Protocol" (Inhaler Trial protocol, page 2).

"Participant Identification Centre (PIC)"

Each of which shall be a "Party" and collectively the "Parties"

Whereas

- A. The Sponsor is a technology company involved in the research, development, manufacture and sale of technology for the use in life science;
- B. The Participating Organisation is contracted to act as the Processor of the Sponsor (as Controller) for Personal Data Processed for the purpose of the Clinical Trial;
- C. The Participating Organisation wishes to sub-contract with the PIC to undertake Data Processing for the purpose of identifying potential Clinical Trial Subjects for the Clinical Trial.

It is therefore, agreed that the following terms and conditions shall apply to the conduct of the Data Processing undertaken by the PIC for the purpose of the Clinical Trial (as further defined below):

1. Definitions

- 1.1 In this Agreement, the following words shall have the following meanings:
 - Affiliate

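### Five of the ten NHS-use items in Appendix 7 name the wrong disease in their zero instruction, so some events may be undercounted in two secondary outcomes

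*Protocol*

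**What the plan says.** Section 4.2 lists two secondary outcomes that rest on patient-reported counts: "Differences in the number of emergency admissions between the intervention and control group over 26 weeks" and "Differences in the utilisation of NHS resources between the intervention and control group over 26 weeks". The same section points to Appendix 7 as the full survey that participants will receive. Section 10.1 has every enrolled patient complete it at baseline, 13 weeks and 26 weeks.

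Each form in Appendix 7 ends with five NHS-use items. Each item is a question about events in the past three months, an instruction on when to enter zero, and a free-text box.

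- Asthma item 11 asks "Roughly how many times have you stayed in hospital in relation to your asthma over the past 3 months, if at all". Its instruction reads "Put '0' if you haven't had to stay in hospital at all in relation to your COPD over the past 3 months".
- COPD item 15 asks about an "emergency GP appointment with your own GP or a walk-in centre in relation to your COPD over the past 3 months, if at all", and COPD item 18 asks how often the patient has "visited Accident & Emergency (A&E) in relation to your COPD over the past 3 months, if at all". Items 16 and 17 (NHS 111 and Urgent Care Centre) are built the same way. All four carry the instruction "Put '0' if you haven't had to use this service at all in relation to your asthma over the past 3 months".

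**The concern.** In five items the question and its instruction refer to different diseases. An asthma patient without COPD never has a COPD-related stay, so the literal instruction on item 11 is to enter 0 whatever happened. A COPD patient without asthma meets the same problem on items 15 to 18.

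A zero entered this way cannot be told from a true zero afterwards. Section 11.1 mentions medical records, but the extraction described in sections 7.5 and 10.1 is of prescription data, and section 11.3 says that nothing beyond survey and prescription data will be available. No planned source would reveal or repair a false zero. At stake is the ability of two secondary outcomes to show a difference if there is one.

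**Working it through.** **Step 1: compare each question with its own instruction (Appendix 7).**

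| Form | Item | Subject | Disease in question | Disease in zero instruction | Match |
|---|---|---|---|---|---|
| Asthma | 11 | Hospital stay | Asthma | COPD | No |
| Asthma | 12 | Emergency GP or walk-in | Asthma | Asthma | Yes |
| Asthma | 13 | NHS 111 | Asthma | Asthma | Yes |
| Asthma | 14 | Urgent Care Centre | Asthma | Asthma | Yes |
| Asthma | 15 | A&E | Asthma | Asthma | Yes |
| COPD | 14 | Hospital stay | COPD | COPD | Yes |
| COPD | 15 | Emergency GP or walk-in | COPD | Asthma | No |
| COPD | 16 | NHS 111 | COPD | Asthma | No |
| COPD | 17 | Urgent Care Centre | COPD | Asthma | No |
| COPD | 18 | A&E | COPD | Asthma | No |

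Mismatches: 1 of 5 on the asthma form, 4 of 5 on the COPD form, 5 of 10 in all. The hospital-stay instruction names COPD on both forms and the service-use instruction names asthma on both forms. That pattern suggests text copied from one form to the other rather than damage in the file.

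**Step 2: who can be misrecorded.** A patient with no event enters 0 under either reading, which is correct. A patient with an event who answers the question enters the true count. Only a patient with an event who obeys the instruction over the question enters a false 0. Patients with both diseases are assigned the CAT (section 4.2 and Appendix 2), so they apparently receive the COPD form. An instruction about asthma does not force a zero for them, and their answers are harder to predict.

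**Step 3: effect on the arm comparison.** The protocol gives neither event rates nor the share of patients who would follow the instruction, so this is an illustration. Let f be that share among single-disease patients with events on an affected item. Assume f is the same in both arms and unrelated to the number of events. Let the true count have mean μ and variance σ².

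- Recorded mean = (1 − f)μ in each arm.
- Recorded mean difference = (1 − f) × true mean difference.
- Ratio of the two means: unchanged, because 1 − f cancels.
- Recorded variance = (1 − f)(σ² + μ²) − (1 − f)²μ² = (1 − f)(σ² + fμ²), which is at least (1 − f)σ².
- The standard error therefore falls by no more than a factor √(1 − f), while the difference falls by 1 − f. The ratio of difference to standard error is multiplied by at most (1 − f)/√(1 − f) = √(1 − f).

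| f (assumed) | Mean difference multiplied by | Difference/SE multiplied by at most |
|---|---|---|
| 0 | 1 | 1 |
| 0.25 | 0.75 | √0.75 = 0.87 |
| 0.50 | 0.50 | √0.50 = 0.71 |
| 1 | 0 | all signal lost |

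These factors apply to an affected item on its own form. If the two forms are pooled, one form's item is sound, so for effects in the same direction the pooled difference is multiplied by something between 1 − f and 1.

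**Step 4: a separate check of outcome against item.** The section 4.2 outcome counts emergency admissions. Asthma item 11 and COPD item 14 count any hospital stay related to the disease, planned or not. The A&E items (asthma 15, COPD 18) count visits, which are not admissions.

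**The case against.** The strongest reply is that every question names the right disease, each form concerns one condition, and the box takes a free-text number. A patient who was in hospital with asthma may simply answer the question and overlook the instruction. This stands: the documents do not show how many would do otherwise, and f could be near 0.

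It is also fair that the primary outcome (MARS-5), the ACT and CAT, the prescription outcome and the sample size, which is based on the CAT, are untouched.

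Three stronger readings are tempting, and the documents support none of them.

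- A reader might infer that the admission count is wrong for all asthma patients. It is not: most zeros would be true zeros, and only patients with events who follow the instruction are affected.
- A reader might infer that COPD admissions are affected too. COPD item 14 is consistent.
- A reader might infer bias towards one arm, because pooled counts mix sound and faulty items. Randomisation is individual and both arms receive the same forms, so nothing in the protocol points to one arm being favoured. Error of this kind in a baseline count makes it a weaker covariate but does not bias the randomised comparison.

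What the reply does not remove is that the two halves of five items contradict each other, that a false zero cannot be detected later, and that the correction is very cheap.

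**Conclusion.** The defect is real and of limited reach. Five of the ten NHS-use items carry an instruction that contradicts their question: the hospital-stay item on the asthma form and all four service-use items on the COPD form. Some events may be undercounted in two secondary outcomes, at all three surveys. Under an equal f in both arms, the absolute mean difference on an affected item is multiplied by 1 − f. The loss runs from none at f = 0 to complete at f = 1, and the protocol does not say where in that range the trial would lie. A ratio of means would not shift but would be less precise. The expected result is dilution and reduced power, not a false finding for either arm.

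The gap between hospital stays and emergency admissions is a separate and smaller point. It holds whichever disease the instruction names.

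**What to change.** - In Appendix 7 and the live survey, change the disease in the zero instruction of asthma item 11 to asthma, and in COPD items 15 to 18 to COPD.
- Do this before the form goes live. If it is already in use, make one dated change in both arms at the same time and flag responses given on the old wording, so that results for these items can be read by form version.
- Separately, either reword asthma item 11 and COPD item 14 to ask about unplanned (emergency) stays, or rename the section 4.2 outcome as hospital stays related to the disease.

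The cost is five single-word corrections, a choice of wording for two items or one outcome, and a minor amendment. The sample size, visit schedule and primary analysis do not change.

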3.2 Processing of Clinical Trial Subject Personal Data

- 3.2.1 For the purpose of the Data Protection Laws and Guidance, the Sponsor is the Controller, the Participating Organisation is the Processor and the PIC is the Sub-Processor of the Participating Organisation in relation to the Processing of Personal Data for the purpose of the Clinical Trial.
- 3.2.2 The PIG's Processing of Personal Data, as a Sub-Processor of the Participating Organisation, shall be governed by this Agreement, including the Protocol, which sets out the subject matter, duration, nature, and purpose of the Processing, type of Personal Data and categories of data subjects, and obligations and rights of Sponsor as Controller and Participating Organisation as Sub-Processor.
- 3.2.3 The PIC is the Controller of Personal Data that it processes for purposes other than the Clinical Trial, e.g. the provision of medical care.
- 3.2.4 The PIC, in its role as Processor of the Personal Data under Clause 3.2.1, agrees to only Process Personal Data for and on behalf of the Sponsor in accordance with the documented instructions of the Sponsor and/or Participating Organisation, including with regard to transfers of personal data to a third country or an international organisation. If the PIC is required by law to otherwise Process the Personal Data, the PIC shall notify the Participating Organisation before undertaking the Processing, unless such notification is prohibited on important grounds of public interest in accordance with GDPR Article 28(3)(a). In the case of such prohibition, the PIC shall notify the Participating Organisation as soon as possible once the prohibition is lifted, if it is lifted.
- 3.2.5 The PIC agrees to comply with the obligations applicable to Processors described by Article 28 of the GDPR, as well as those additional obligations required by Participating Organisation pursuant to this Agreement, including but not limited to the following:
 - a. implementing and maintaining appropriate technical and organisational security measures for Personal Data Processed in its systems, in keeping with its

obligations as an NHS organisation, thereby providing guarantee to the Sponsor pursuant to GDPR Article 28(1);

- b. ensuring that Personnel authorised to Process Personal Data have committed themselves to confidentiality or are under an appropriate statutory obligation of confidentiality (Article 28(3)(b));
- c. taking all measures required by GDPR Article 32 in relation to the security of processing (GDPR Article 28(3c));
- d. complying with the conditions described in GDPR Article 28(2) and (4) for engaging another Processor (GDPR Article 28(3d));
- taking into account the nature of the Processing, assist the Sponsor and/or the Participating Organisation, by appropriate technical and organisational measures, insofar as this is possible, to respond to requests for exercising Data Subjects' rights (GDPR Article 28(3e));
- f. assisting the Controller, to ensure compliance with the obligations pursuant to GDPR Articles 32 to 36, taking into account the nature of the Processing and the information available to the PIC (GDPR Article 28(3f));
- g. maintaining a record to demonstrate compliance with this Clause and Data Protection Laws and Guidance, including the records required pursuant to GDPR Article 30(2);
- h. in the event of any Personal Data Breach by the PIC as a Sub- Processor of the Participating Organisation, the PIC shall: (i) promptly and without undue delay following discovery of such Personal Data Breach, send written notice of the incident via e-mail to [contact] (ii) not make any statements or notifications about the Personal Data Breach, as it relates to the Processing for the purpose of the Clinical Trial, to any individual affected by the incident, the public or any third party without Sponsor or Participating Organisations prior written approval; and (iii) immediately take steps to investigate and mitigate the Personal Data Breach and reasonably cooperate with Sponsor and the Participating Organisation.
- 3.2.6 In furtherance of its obligations under Article 28 GDPR, the PIC agrees that it will not engage another Processor for the purpose of the Clinical Trial without the prior written authorisation of the Sponsor or Participating Organisation (GDPR Article 28(2)).
- 3.2.7 At the expiry or lapse of this Agreement, the PIC shall, at the choice of the Participating Organisation, destroy or return all Personal Data to the Sponsor or Participating Organisation unless there is a legal requirement for retention and storage

(GDPR Article 28(3g)) and/or where that Personal Data is held by the PIC as Controller for its own purpose(s).

3.2.8 The PIC will:

- a. ensure that its Personnel do not Process Personal Data except in accordance with the Protocol and this Agreement;
- b. take all reasonable steps to ensure the reliability and integrity of any of its Personnel who have access to the Personal Data and ensure that the Personnel:
 - (i) are aware and comply with the PIG's duties under this Clause 3 (Confidentiality and Data Protection);
 - (ii) are subject to mandatory training in their information governance responsibilities and have appropriate contracts, including sanctions, including for breach of confidence or misuse of Personal Data; and
 - (iii) are informed of the confidential nature of the Personal Data and understand their responsibilities for information governance, including their obligation to Process Personal Data securely and to only disseminate or disclose it for lawful and appropriate purposes.

3.2.9 The PIC agrees to:

- a. provide the Sponsor and/or the Participating Organisation with evidence of its compliance with the obligations set out in this Agreement, or, at the Sponsor and/or Participating Organisation's discretion and on reasonable notice, to allow the Sponsor, Participating Organisation or a third party appointed by the Sponsor or Participating Organisation, to audit the PIG's compliance with the obligations described in this Agreement, Data Protection Legislation and Guidance (including but not limited to Article 28 GDPR), subject to the Sponsor, Participating Organisation or appointed third party, complying with all relevant health and safety and security policies of the PIC;
- obtain prior written agreement of the Sponsor or Participating
 Organisation to Process Personal Data outside of the UK and the EEA.
- 3.2.10 In addition to the PIG's obligations under Clause 3.2.9.b, where the PIG, acting as the Participating Organisation's Sub-Processor, Processes Personal Data outside of the UK and the EEA, the PIC warrants that it does so in compliance with the Data Protection Laws and Guidance.

4. Intellectual Property

- 4.1 All Intellectual Property Rights and Know-How owned by or licensed to the Sponsor, Participating Organisation or Affiliate(s) prior to and after the date of this Agreement, other than any Intellectual Property Rights and Know-How arising from the Clinical Trial, are and shall remain the property of the Sponsor, Participating Organisation or Affiliate(s), as the case may be.
- 4.2 All Intellectual Property Rights and Know-How owned by or licensed to the PIC prior to and after the date of this Agreement, other than any Intellectual Property Rights and Know-How arising from the Clinical Trial, are and shall remain the property of the PIC.
- 4.3 All Intellectual Property Rights and Know-How arising from and relating to the Clinical Trial, the IMP (including but not limited to its formulation and use alone or in combination with other drugs), and/or the Protocol, but excluding any clinical procedure and improvements thereto that are clinical procedures of the PIC, shall vest in the Sponsor in accordance with Clauses 4.4 and 4.5 of this Agreement.
- 4.4 In accordance with Clause 4.3, the PIC hereby assigns, and shall procure that its Agents assign, its rights in relation to all Intellectual Property Rights and Know- How, falling within Clause 4.3, to the Sponsor or its nominee. At the request and expense of the Sponsor, the PIC shall execute, and shall procure that its Agents shall execute, all such documents and do all such other acts as the Sponsor may reasonably require in order to vest fully and effectively all such Intellectual Property Rights and Know-How in the Sponsor or its nominee.
- 4.5 PIC shall and will ensure that the Personnel promptly disclose to the Participating Organisation any Know-How generated pursuant to this Agreement and falling within Clause 4.3 and undertakes not to use or disclose such Know-How other than for the purposes of this Agreement.
- 4.6 Nothing in this Clause 4 shall be construed so as to prevent or hinder the PIC from using its Know-How generated during the performance of the Clinical Trial in the furtherance of its normal activities, to the extent that such use does not result in the disclosure or misuse of Confidential Information or the infringement of any Intellectual Property Right or Know-How of the Sponsor or Participating Organisation.

5. Sign Off

Refer to page 2 "Principal Investigator and Service Agreement for the Protocol" of the Inhaler Trial (IRAS 316452) protocol.
